#### 11.4.2 Statistical / Analysis Issues

Not applicable

#### 11.4.2.1 Adjustments for Covariates

There were no covariate adjustments made during statistical analysis.

#### 11.4.2.2 Handling of Dropouts or Missing Data

Pharmacokinetic analyses included data from samples of subjects who completed both study periods.

The 90% confidence intervals are based on those subjects who completed both the periods of the study.

#### 11.4.2.3 Interim Analyses and Data Monitoring

Not applicable.

#### 11.4.2.4 Multicentre Studies

This was a single center study.

Protocol No. C-CMP-SPI-001

Confidential

Page 48 of 64

(Fasting Condition)

Confidential

## 11.4.2.5 Multiple Comparison/Multiplicity

Not applicable

## 11.4.2.6 Use of an "Efficacy Subset" of Subjects

Not applicable

## 11.4.2.7 Active- Control Studies Intended to Show Equivalence

Not applicable

## 11.4.2.8 Examination of Subgroups

Not applicable

## 11.4.3 Tabulation of Individual Response Data

The individual concentration data of digoxin was provided in Appendix 16.2.6.

## 11.4.4 Drug Dose, Drug Concentration, and Relationships to Response

Not applicable

## 11.4.5 Drug-Drug and Drug-Disease Interactions

Not applicable

## 11.4.6 By – Subject Displays

Individual plasma Concentrations Versus Time (Linear plots) for digoxin was provided in Appendix 16.2.6.

## 11.4.7 Pharmacokinetic Conclusions

The % Treatment A / Treatment B ratio of digoxin was 64.597% and 84.224% for  $C_{max}$  and AUC0.96 respectively. The lower and the upper limits at 90% confidence interval were 54.18% - 77.02% and 77.45% - 91.59% for  $C_{max}$  and AUC0.96 respectively, which is not within the standard equivalence limit of 80.00-125.00%. Based on the above results presence of drug-drug interaction is established between digoxin and spironolactone.

By comparing  $C_{max}$  and  $AUC_{0.96}$  plasma values of Treatment A and Treatment B, we conclude that these values were increased by 35% and 16% respectively for Treatment B

The Renal clearance (CLR)/Percent Recovered and unchanged drug excreted in urine (fe)/ Amount Recovered of digoxin was comparable for the Treatment A and Treatment B. The geometric mean Renal clearance (CLR)/Percent Recovered was 49.042 and 49.410 for Treatment A and Treatment B respectively. The geometric mean unchanged drug excreted in urine (fe)/ Amount Recovered was 122606.02 and 123523.87 for Treatment A and Treatment B respectively.

Protocol No. C-CMP-SPI-001

Confidential

(Fasting Condition)

Confidential

By comparing these values, we conclude that there is not much difference between Treatment A and Treatment B, with respect to Renal clearance (CLR)/Percent Recovered and unchanged drug excreted in urine (fe)/ Amount Recovered.

Confidential

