Treatment B	Median	2422.385	17151.091	0.750
Tr	Max	5044.130	23997.624	3.500
	G. Mean	2254.118	15996.644	0.810
	G.mean %CV	45.789	28.453	44.310

Table 10: Summary Statistics for Untransformed Pla	sma PK Parameters of digoxin Per
Treatment	

Treatment A: LANOXIN® (digoxin) USP 250 mcg (substrate drug)

Treatment B: LANOXIN® (digoxin) USP 250 mcg + Spironolactone Oral Suspension 100 mg (Carospir® Oral Suspension 20 mL of 25 mg / 5 mL)

The median time to reach peak plasma concentration  $(T_{max})$  for digoxin was 0.750 hr and 0.750 hr following administration of Treatment A and Treatment B respectively. The  $T_{max}$  ranged from 0.500 to 1.330 hr and 0.500 to 3.500 hr for Treatment A and Treatment B respectively.

The exposure ( $C_{max}$  and  $AUC_{0.96}$ ) of digoxin was not comparable for the Treatment A and Treatment B. The geometric mean  $C_{max}$  was 1456.085 and 2254.118 ng/mL for Treatment A and Treatment B respectively. The geometric mean  $AUC_{0.96}$  was 13473.043 and 15996.644 ng.hr/mL for Treatment A and Treatment B respectively.

(Fasting Condition)

Confidential

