### **Pharmacokinetics**

Typical pharmacokinetic endpoints for DDI studies include changes in drug exposure parameters such as  $C_{max}$  and  $AUC_{0.72}$ . Pharmacokinetic sampling times should be sufficient to characterize the  $C_{max}$  and  $AUC_{0.72}$ . The sampling times for single-dose studies should be planned so that the mean difference between the  $C_{max}$  and  $AUC_{0.72}$  is less than 20 percent. Pharmacokinetic results of DDI study will be reported as the geometric mean ratio of the observed pharmacokinetic exposure measures with and without the perpetrator drug and include the associated 90 percent confidence interval. Observed variability of the interaction will also be reported.

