### 4.2 Randomization

The order of receiving the treatment A and treatment B for each subject during the study will be determined randomly. According to the randomization schedule, subjects will receive the assigned formulation in each period, with the possible sequences 'AB' or 'BA' (where A = substrate and B = substrate & perpetrator). Equal allocation of subjects to each sequence will be ensured. The randomization will be balanced and the randomization schedule as well as the dispensing records will be kept in the drug store under controlled access. The study personnel involved in dispensing (pharmacist) and the Principal Investigator will be accountable for ensuring compliance to randomization schedule. Randomization schedule will be generated using SAS® software 9.3 or higher.

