#### 10.5 Ratio analysis

The comparison of interest is Treatment (A) Vs Treatment (B), so the ratios will be of the form: Treatment (A/B).

Ratio of least squares means of Treatment A & B will be computed for Intransformed pharmacokinetic parameters  $C_{max}$  and AUC0.96. Ratio analysis will be reported in percentage for In-transformed pharmacokinetic parameters ( $C_{max}$  and AUC0.96) for Digoxin.

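### The report understates the rise in digoxin exposure with spironolactone: its own geometric means give +55% (Cmax) and +19% (AUC0-96), not +35% and +16%

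*Protocol*

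**What the plan says.** Protocol Section 4.2 defines the arms: "where A = substrate and B = substrate & perpetrator". Section 10.5 fixes the direction of the comparison: "The comparison of interest is Treatment (A) Vs Treatment (B), so the ratios will be of the form: Treatment (A/B". The planned ratio is therefore exposure without spironolactone over exposure with it. The SAP refers to a ratio between the two treatments and does not state a direction.

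The Pharmacokinetics text in the protocol's Background (Section 2) says results will be reported as the "geometric mean ratio of the observed pharmacokinetic exposure measures with and without the perpetrator drug", an order that puts the spironolactone arm first.

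Report Section 11.4.1 states that geometric mean Cmax "was 1456.085 and 2254.118 ng/mL for Treatment A and Treatment B respectively" and that geometric mean AUC0-96 "was 13473.043 and 15996.644 ng.hr/mL for Treatment A and Treatment B respectively". Section 11.4.7 gives the ratios: "The % Treatment A / Treatment B ratio of digoxin was 64.597% and 84.224" (both in percent, Cmax then AUC0-96). It then concludes that "we conclude that these values were increased by 35% and 16% respectively for Treatment B". The same sentence appears in the Synopsis conclusion and in Section 13.

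**The concern.** An increase for Treatment B takes Treatment A, digoxin without spironolactone, as its base. The stated 35% and 16% look like the complements of the A/B ratios, which take B as their base. They would then describe how much lower exposure is without spironolactone, not how much higher it is with it.

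The size of the interaction is what a reader takes from this study. Protocol Section 3.2 says the study assesses an interaction that raises digoxin levels. Section 10.1 justifies 28 subjects by the need for a reliable estimate of the interaction's magnitude. Section 11.2 calls digoxin a narrow therapeutic index drug. Section 2.2.4 describes the carvedilol interaction as a rise of about 15% in digoxin concentration, and a reader would naturally set the headline percentages beside a figure of that kind. The report gives no B/A ratio or interval, so the only increase it offers for quotation is the one in this sentence.

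**Working it through.** **Inputs**

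| | Cmax | AUC0-96 | Source |
|---|---|---|---|
| Geometric mean, A | 1456.085 | 13473.043 | Tables 10 and 11 |
| Geometric mean, B | 2254.118 | 15996.644 | Tables 10 and 11 |
| A/B, stated | 64.597% | 84.224% | Table 11 |
| 90% CI of A/B, stated | 54.18–77.02% | 77.45–91.59% | Table 11 |
| Intra-subject CV | 40.07% | 18.56% | Table 11 |
| Subjects analysed | 28 | 28 | Section 11.1 |

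**Step 1: reproduce the ratios and intervals.**

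- Cmax: A/B = 1456.085/2254.118 = 0.64597.
- AUC0-96: A/B = 13473.043/15996.644 = 0.84224.
- 90% CI = exp{ln(A/B) ± t(0.95; 26) × √ln(1 + CV²) × √(2/28)}, with residual df = 28 − 2 = 26. This gives 54.18–77.02% for Cmax and 77.45–91.59% for AUC0-96, as printed.

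The analysis behind the table is internally consistent.

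**Step 2: reproduce the stated increases.**

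- 1 − A/B for Cmax = 1 − 0.64597 = 35.4%.
- 1 − A/B for AUC0-96 = 1 − 0.84224 = 15.8%.

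These round to the report's 35% and 16%, so the sentence uses the complement of A/B.

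**Step 3: compute the increase for B over A.**

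- Cmax: B/A − 1 = 2254.118/1456.085 − 1 = 1.548 − 1 = +54.8%.
- AUC0-96: B/A − 1 = 15996.644/13473.043 − 1 = 1.187 − 1 = +18.7%.

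As a cross-check, a 35% rise from 1456.085 would give 1.35 × 1456.085 ≈ 1966, but the reported mean for B is 2254.118.

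**Step 4: invert the confidence limits.** The upper A/B limit becomes the lower B/A limit, and vice versa.

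- Cmax: 1/0.7702 = 129.8% and 1/0.5418 = 184.6%.
- AUC0-96: 1/0.9159 = 109.2% and 1/0.7745 = 129.1%.

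**Step 5: see whether another summary gives 35% and 16%.**

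| Basis (Table 10) | Cmax, B/A − 1 | AUC0-96, B/A − 1 |
|---|---|---|
| Geometric means | +54.8% | +18.7% |
| Arithmetic means (1530.188, 2432.908; 13715.974, 16551.500) | +59.0% | +20.7% |
| Medians (1429.822, 2422.385; 13440.345, 17151.091) | +69.4% | +27.6% |

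None does.

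**Step 6: size of the understatement.** For Cmax, 54.8 − 35.4 = 19.4 percentage points (20 on the rounded figures). For AUC0-96, 18.7 − 15.8 ≈ 3 points. Over one third of the Cmax rise is lost (19.4/54.8 = 35%).

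**The case against.** The strongest reply is that A/B was prespecified, is a legitimate direction, and is used consistently in the tables and text. The Background wording names no numerator. It also sits in generic text that refers to AUC0-72, which is not this study's endpoint, so it is weak ground for calling Section 10.5 inverted. The decision rule is unaffected, because 80.00–125.00% is symmetric on the log scale. The geometric means appear beside the sentence in the Synopsis and Section 13, so a careful reader can recover the right figure. Section 3.2 asks whether there is an interaction, not how large it is. The AUC discrepancy is small.

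Much of this stands. The A/B direction is not itself an arithmetic error; the error is reading its complement as a rise over A. The interaction conclusion is safe, and the material discrepancy is in Cmax. What does not stand is the suggestion that this makes the sentence acceptable. It is false on the report's own means, nothing elsewhere corrects it, and Section 10.1 does make magnitude a purpose of the study. The choice of A/B also made the slip easy, since it leaves the reader to invert the ratio to obtain the quantity of interest.

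**Conclusion.** The concern holds. With spironolactone, digoxin Cmax rose by 55% (B/A 154.8%, 90% CI 129.8% to 184.6%) and AUC0-96 by 19% (B/A 118.7%, 90% CI 109.2% to 129.1%). The stated 35% and 16% are the reductions from B to A. The result assumes only that the reported geometric means and A/B intervals are correct, and those reproduce from the reported variability. Both B/A intervals extend beyond 125.00%, so the finding of an interaction stands. Only its stated size is wrong, and that must be corrected because it is the headline result.

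**What to change.** 1. In the Synopsis conclusion, Section 11.4.7 and Section 13, replace the increases of 35% and 16% with 55% and 19%, and state that the base is digoxin alone.
2. Add B/A with its 90% CI to the Synopsis ratio table and to Table 11: Cmax 154.8% (129.8–184.6%), AUC0-96 118.7% (109.2–129.1%). Carry the same figures into the drug-drug interaction text of Section 11.4.1, which now describes only A/B.
3. Define the ratio in Section 10.5 as Treatment B / Treatment A, in line with the with-and-without wording of the Background. As the study is already reported, the prespecified A/B results can stay alongside, with a note that B/A is their reciprocal and not a new analysis.

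The cost is three corrected sentences, added entries in two tables and a short note on direction. No model is refitted and no test result changes.

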#### Table 9: Subject disposition (All Subjects)

	Sequence 1	Sequence 2	All
	AB	BA	Subjects
Subjects			
Randomized	14	14	28
Completed	14	14	28
Discontinued	00	00	00

Treatment A: LANOXIN® (digoxin) USP 250 mcg (substrate drug)

Treatment B: LANOXIN® (digoxin) USP 250 mcg + Spironolactone Oral Suspension 100 mg (Carospir® Oral Suspension 20 mL of 25 mg / 5 mL)

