## Table 12 Summary Statistics for Untransformed Urine PK Parameters of digoxin Per Treatment

Treatment	Statistics	Renal clearance (CLR)/Percent Recovered	unchanged drug excreted in urine (fe)/ Amount Recovered
	N	28	28
	Mean	54.687	136717.72
I A	SD	29.158	72895.492
Treatment	Min	22.180	55449.800
atm	Median	46.111	115277.98
Tre	Max	147.642	369104.30
	G. Mean	49.042	122606.02
	G.mean %CV	48.257	48.257

Treatment	Statistics	Renal clearance (CLR)/Percent Recovered	unchanged drug excreted in urine (fe)/ Amount Recovered
	N	28	28
	Mean	53.378	133446.07
B	SD	21.256	53141.044
Jeni	Min	21.641	54103.200
Ireatment	Median	51.185	127962.08
Tre	Max	95.602	239003.90
	G. Mean	49.410	123523.87
	G.mean %CV	42.201	42.201

Treatment A: LANOXIN® (digoxin) USP 250 mcg (substrate drug)

Treatment B: LANOXIN® (digoxin) USP 250 mcg + Spironolactone Oral Suspension 100 mg (Carospir® Oral Suspension 20 mL of 25 mg / 5 mL)

The Renal clearance (CLR)/Percent Recovered and unchanged drug excreted in urine (fe)/ Amount Recovered of digoxin was comparable for the Treatment A and Treatment B. The geometric mean Renal clearance (CLR)/Percent Recovered was 49.042 and 49.410 for Treatment A and Treatment B respectively. The geometric mean unchanged drug excreted in urine (fe)/ Amount Recovered was 122606.02 and 123523.87 for Treatment A and Treatment B respectively.

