## 12. SAFETY EVALUATION

## **12.1 EXTENT OF EXPOSURE**

On Day 6, subjects were on fast for 10.00 hours prior to dose administration and for 4.00 hours post dose in each study period. Subjects were administered a single dose of either Treatment A or Treatment B as per randomization scheme with about 240 mL of water for the subjects who were assigned A; 120 mL for LANOXIN® (digoxin) USP 250 mcg and 120 mL for Spironolactone Oral Suspension 100 mg (Carospir® Oral Suspension 20 mL of 25 mg / 5 mL) for the subjects who were assigned B, at ambient temperature in sitting position in each study period. Oral cavity check was done immediately after drug administration to assess the compliance to this procedure.

Total 28 subjects had completed the clinical phase of the study successfully. Plasma and urine samples of 28 subjects were analyzed and plasma and urine concentration data of all 28 subjects was considered to draw statistical conclusion.

The duration of clinical phase was 39 days, including the washout period of 28 days between each study period.

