By comparing these values, we conclude that there is not much difference between Treatment A and Treatment B, with respect to Renal clearance (CLR)/Percent Recovered and unchanged drug excreted in urine (fe)/ Amount Recovered.

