#### 10.7 Criteria for evaluation

The presence or absence of DDI between two treatments (A and B) will be based on the statistical results of 90% confidence interval for the ratio of the geometric least squares mean for log-transformed pharmacokinetic parameters  $C_{max}$  and AUC0-96 for Digoxin.

Absence of drug-drug interaction will be established if the 90% CI for the ratio of population geometric means between two treatments (A and B), based on log-transformed data, present in the equivalence limits of 80.00 - 125.00% for Cmax and AUC0-96.

Summary statistics of pharmacokinetic profile of Digoxin (substrate drug) in the presence and absence of spironolactone (perpetrator) will be provided based on plasma and urine data. Renal clearance (CLR)/ Percent Recovered and unchanged drug excreted in urine ( $f_e$ )/Amount Recovered for Digoxin will also be measured

Protocol for Drug-Drug Interaction Study of Spironolactone and Digoxin (Fasting Condition) Confidential

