Pharmacokinetic data of those subjects will be tabulated and reported in the study report as a separate table. However, the data of such subjects will also be considered for statistical analysis if the 3 consecutive post dose samples are the last three samples of elimination phase.

If the pre-dose concentration appears to be > 5% of the Cmax in any subject at any period, the data of such a subject will be excluded from the statistical analysis.

STATISTICAL ANALYSIS

Statistical analysis will be performed by using SAS statistical software version 9.3 or above.

Descriptive statistics of all the pharmacokinetic parameters will be computed and reported for digoxin.

The log-transformed pharmacokinetic parameters Cmax and AUC0-96 were analysed using Type III sum of squares, with the main effects of formulation, period, sequence and subjects nested within sequence as random effect.

Statistical analysis was performed using SAS® package (SAS Institute Inc., USA, Version 9.3).

The presence or absence of DDI between the two treatments (A and B) was concluded based on the statistical results of 90% confidence interval for the ratio of the geometric least squares mean for log-transformed pharmacokinetic parameters Cmax and AUC0-96 for Digoxin. Absence of drug-drug interaction would be established if the 90% CI for the ratio of population geometric means of log-transformed data of Cmax and AUC0-96 between two treatments (A and B), were in the equivalence limits of 80.00 - 125.00% for Digoxin.

Renal clearance (CLR)/ Percent Recovered and unchanged drug excreted in urine (fe)/Amount Recovered for Digoxin in the presence and absence of spironolactone was provided as supportive data.

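### Renal clearance is called comparable from geometric means alone; clearance as the plan defines it (amount/AUC) is about 15% lower with spironolactone, and comparability is not shown

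*Protocol*

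**What the plan says.** Protocol section 3.1 lists measuring renal clearance/percent recovered and unchanged drug excreted/amount recovered, with and without spironolactone, as a secondary objective.

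For plasma Cmax and AUC0-96, section 10.7 accepts absence of interaction only if the 90% CI for the geometric mean ratio lies within 80.00-125.00%. For urine it offers only description, in a sentence that covers both kinds of sample: "Summary statistics of pharmacokinetic profile of Digoxin (substrate drug) in the presence and absence of spironolactone (perpetrator) will be provided based on". The SAP says that the urine measures "for Digoxin in the presence and absence of spironolactone was provided as supportive data". Both documents define renal clearance as amount excreted divided by AUC, over 0-240 h.

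The study report, bound in the same file as the protocol, goes further. Under Table 12 it states that renal clearance and unchanged drug "excreted in urine (fe)/ Amount Recovered of digoxin was comparable for the Treatment A and Treatment B". Section 11.4.7 then says: "By comparing these values, we conclude that there is not much difference between Treatment A and Treatment B, with respect to Renal clearance". Section 13 repeats this, and the synopsis conclusion repeats the comparability statement. Section 12.1 says "plasma and urine concentration data of all 28 subjects was considered to draw statistical conclusion", but no inferential analysis of urine is shown.

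**The concern.** Finding two means close together does not show that two treatments are equivalent. The report holds the plasma data to an interval inside a stated margin. For urine it reaches a conclusion of the same kind with neither interval nor margin.

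The urine result bears on how the rise in digoxin is read. Protocol section 2.2.4, as general background, lists spironolactone among drugs that raise digoxin by lowering its clearance and/or volume of distribution. A statement that renal clearance was unchanged steers the reader away from a renal contribution. The report's own means do not support that statement for clearance: the amount excreted is flat while AUC rises, so amount divided by AUC must fall.

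**Working it through.** **Inputs.** All are from the study report, except two correlations that the documents do not give.
- n = 28, with allocation in Table 9 "Randomized 14 14 28"; residual df 26; t(0.95, 26) = 1.706.
- Amount recovered, geometric means (Table 12): A 122606.02, B 123523.87. Geometric CVs: 48.257% and 42.201%.
- AUC0-96, geometric means (Table 11): A 13473.043, B 15996.644. Intra-subject CV: 18.56%.
- Assumed: ρ, the correlation between a subject's log amounts in the two periods (0 to 0.7), and c, the correlation between the amount and AUC log-differences (0 to 0.5).

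**1. Reproduce the plasma interval.** For AUC0-96, s = √ln(1 + 0.1856²) = 0.1840 and SE = 0.1840 × √(2/28) = 0.0492. Then 84.224% × exp(±1.706 × 0.0492) = 77.45% to 91.59%, as printed. The same method gives 54.18% to 77.02% for Cmax, also as printed.

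**2. Identify the tabulated quantity.** The dose is 250 mcg = 250,000 ng. 122606.02/250,000 = 49.042% and 123523.87/250,000 = 49.410%. These are the two means printed under the renal clearance heading, and the CVs in both columns are identical. The column is percent of dose recovered, not amount/AUC.

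**3. Amount (= percent) recovered.** B/A = 123523.87/122606.02 = 1.0075. The log SDs are √ln(1 + 0.48257²) = 0.4575 and √ln(1 + 0.42201²) = 0.4048. The SD of the log difference is √(0.4575² + 0.4048² − 2ρ × 0.4575 × 0.4048), and SE = SD/√28. At ρ = 0, SD = 0.611 and SE = 0.1155.

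**4. Renal clearance as amount/AUC0-96.** Sampling stops at 96 h, so the 0-240 h version cannot be computed. Both sets of geometric means come from the same 28 subjects, so the ratio of means is exact and units cancel:

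B/A = 1.0075 × (13473.043/15996.644) = 1.0075 × 0.8422 = 0.849.

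The SD of the AUC log difference is 0.1840 × √2 = 0.260. The SD for clearance is √(SD_amount² + 0.260² − 2c × SD_amount × 0.260).

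| ρ | Amount, 90% CI | Clearance, c = 0 | Clearance, c = 0.3 | Clearance, c = 0.5 |
|---|---|---|---|---|
| 0 | 0.827-1.227 | 0.685-1.051 | 0.702-1.026 | 0.715-1.007 |
| 0.3 | 0.854-1.188 | 0.705-1.021 | 0.722-0.997 | 0.736-0.979 |
| 0.5 | 0.876-1.159 | 0.721-0.999 | 0.738-0.976 | 0.751-0.959 |
| 0.7 | 0.904-1.123 | 0.740-0.974 | 0.756-0.953 | 0.769-0.937 |

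**5. How far the assumptions matter.** The amount interval stays within 80-125% for any ρ above about −0.20. The clearance lower limit is below 0.80 in all 12 cells. To exceed 0.80, the SD of the log difference must be under 0.183, a within-subject CV of about 13%; AUC0-96 alone has 18.56%. Only jointly extreme correlations reach this: ρ = 0.8 with c = 0.8 gives a lower limit of 0.803, while ρ = 0.7 with c = 0.8 gives 0.795.

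**6. The recovery above 100%.** The Treatment A maximum is 369104.30 ng, or 147.642% of dose. As an illustration only, setting that one value to 100% multiplies B/A by exp(ln(1.47642)/28) = 1.014, giving 0.849 × 1.014 = 0.860. With the narrowest SE in the table (0.058), the lower limit becomes 0.860 × exp(−1.706 × 0.058) = 0.78. If other amounts are also wrong, the effect is unknown.

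**The case against.** The strongest defence is that nothing departs from the plan. The objective is to measure, the urine data are supportive, and summary statistics were promised and delivered. This stands. The 80-125% range was never set for urine and is used here only as the trial's own yardstick.

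A second defence is that the sentence describes the numbers printed beside it, and those numbers would probably pass an interval. This also stands, for recovery. It does not rescue the words about renal clearance, because the printed numbers are not renal clearance by the plan's definition.

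A third is that correcting the column would itself reveal the 15% fall. That is true of the point estimate; the interval would still be missing.

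A reader might also infer that 28 subjects are too few to detect a 20% change in urinary excretion. The documents do not support that as a flat statement. Two-sided 5% power for a 20% fall is 46% at ρ = 0 and 92% at ρ = 0.7, and ρ is not given. Once an interval can be computed, power adds nothing.

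**Conclusion.** The concern holds for renal clearance. The report calls it comparable without an interval. Rebuilt from the printed means as amount/AUC0-96, it is about 15% lower with spironolactone, with a 90% CI between 0.69-1.05 and 0.77-0.94 over the assumed correlations. For amount recovered the statement would likely survive, but this has not been shown.

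Three stronger readings should be resisted:
- **A fall in clearance, or one above 20%, is demonstrated.** It is not: the upper limit lies on either side of 1 depending on the correlations. A fall of more than 20% is merely not excluded, and only for the rebuilt quantity, not for the printed column.
- **The report rules out a renal mechanism.** It does not say so and attributes no mechanism.
- **The interaction finding is undermined.** It rests on Cmax and AUC0-96 alone and is unaffected.

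All urine figures are provisional until the 147.6% recovery is resolved.

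**What to change.** - Resolve the recovery above 100% of dose first.
- Fit the crossover model already used for Cmax and AUC0-96 to log amount recovered 0-96 h and to log(amount 0-96 h/AUC0-96). Report B/A geometric mean ratios with 90% CIs. In the completed report, label this analysis post hoc.
- In the synopsis, the text under Table 12, section 11.4.7 and section 13, replace the comparability wording for renal clearance with the ratio and its interval. Give the interval beside the recovery statement as well.

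The cost is two more runs of an existing SAS model on data already collected, plus edits in four places. The renal conclusion becomes less favourable; the plasma interaction conclusion does not change.
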